- HbA1c ≥ 7 and ≤ 11 % (point-of-care machine or local laboratory [i.e. LabCorp]) (*This criteria only applies to the Main Study, it does *not* apply to the Pilot Study*) This can be omitted if it is not possible to go to a laboratory or come to the clinic because of governmental restrictions such as Stay-at-Home orders, in which case there are no entry restrictions based on HbA1c.
- Willingness and ability to comply with scheduled visits and study procedures
- Willingness to comply with all the study devices during the entire trial (i.e. commercially-available CGM, Fitbit, Companion Medical inPen)
- One month stability on insulin parameters prior to enrollment
- MDI users should use Humalog® and Novolog® insulin to use in study insulin pen
- Type 1 diabetes mellitus diagnosed at least one year prior to enrollment in the study as noted by the following:

Criteria for documented hyperglycemia (at least 1 criterion must be met):

- Fasting glucose ≥ 126 mg/dL-confirmed

- Two-hour Oral Glucose Tolerance Test (OGTT) ≥ 200 mg/dL—confirmed hemoglobin A1c (HbA1c) $\geq 6.5\%$ and documented by history – confirmed Random glucose ≥ 200 mg/dL with symptoms
- No data at diagnosis is available but the participant has a convincing history of hyperglycemia consistent with diabetes

Criteria for requiring insulin at diagnosis (at least 1 criterion must be met):

- Participant required insulin at diagnosis and continually thereafter
- Participant did not start insulin at diagnosis but upon investigator review likely needed insulin (significant hyperglycemia that did not respond to oral agents) and did require insulin eventually and used continually
- The diagnosis of type 1 diabetes mellitus does not require documentation of C-peptide level or islet cell antibody positivity.
- Commitment to maintaining uninterrupted availability via cell phone at all times
- No diabetes complications
- Participants must demonstrate English proficiency and proper mental status and cognition for completion of the study.

- Not currently known to be pregnant, breast feeding, or intending to become pregnant (females). A negative urine pregnancy test will be required for adolescent girls who are able to become pregnant. Participants who become pregnant will be discontinued from the study.
- Ability to access the Internet to provide data to the clinical team or to travel to the research center so that the study equipment can be downloaded.

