- Medication stability in the preceding two months if taking antihypertensive, thyroid, anti-depressant or lipid lowering medication.

2. List the criteria for exclusion for Pilot and Main Study Adolescent Subjects

- Children outside the ages of 12-17 y.o. or those who do not have a parent/guardian willing to participate
- Diabetic ketoacidosis in the past 6 months
- Pregnancy, breast-feeding, or intention of becoming pregnant
- Current or recent alcohol or drug abuse by patient history
- Mental incapacity, unwillingness or language barriers precluding adequate understanding, cooperation, or ability to fill out questionnaires.
- Any skin condition that prevents sensor placement (e.g., bad sunburn, pre-existing dermatitis, intertrigo, psoriasis, extensive scarring, cellulitis)
- Psychiatric disorders that would interfere with study tasks (e.g. cognitive disability, psychiatric hospitalization within 12 months)
- Use of acetaminophen (*this criteria only applies when the CGM version being used is older than the G6*)
- Use of long-acting insulin that is not Lantus or Tresiba
- For subjects who currently use a close-loop insulin pump and CGM: not being willing to turn off the closed-loop function
- Conditions that would make use of a CGM difficult (e.g., blindness, severe arthritis, immobility)
- Cystic fibrosis

- Current use of oral/inhaled glucocorticoids or other medications, which in the judgment of the investigator would be a contraindication to participation in the study
- Any other comorbidity that at the judgment of the investigator may interfere with the participation on the study (i.e. uncontrolled high blood pressure or thyroid disease, current diabetic microvascular complications, current diagnose of gastroparesis)
- Severe hypoglycemia resulting in seizure or loss of consciousness in the 6 months prior to enrollment
- Use of a device that may pose electromagnetic compatibility issues and/or radiofrequency interference with the Dexcom CGM (implantable cardioverter-defibrillator, electronic pacemaker, neurostimulator, intrathecal pump, and cochlear implants)
- Active enrollment in another clinical trial

No eligibility criteria is required for parent(s)/guardian(s) other than the legal relationship and 18+ yo.

3. List any restrictions on use of other drugs or treatments.

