Use of anti-diabetic agents other than short-acting insulin for CSII subjects or long-acting insulin for MDI subjects, including: metformin, sulfonylureas, meglitinides, thiazolidinediones, dipeptidyl peptidase 4 (DPP-4) inhibitors, glucagon-like peptide 1 agonists and alpha-glucosidase inhibitors

Statistical Considerations

1. Is stratification/randomization involved? Yes

► IF YES, describe the stratification/ randomization scheme.

During the main study, up to 210 adolescents, ages 12 years - 17 years (inclusive), will be recruited with one of their parent(s)/guardian(s), 18+ y.o., in each arm. Based on experience, approximately 40 adolescents & 40 parent(s)/guardian(s) in each arm will complete the study (N=80 adolescents and 80 parents, total 160 subjects). Male and female adolescents will be recruited, and all racial/ethnic groups will be eligible for participation. Participants will be recruited in randomization blocks of 4. The goal is to target a minimum of 10 participants in each of the 4 stratification subgroups based on age (12-14 y.o and 15-17 y.o.) and insulin therapy (CSII and insulin pen). ,

► IF YES, who will generate the randomization scheme?

Sponsor
 UVa Statistician. Answer/Response:
 UVa Investigational Drug Service (IDS)
 Other: Center for Diabetes Technology (CDT) personnel

2. What are the statistical considerations for the protocol?

The objectives section and the statistical section should correspond, and any objective for which analysis is unfeasible should be deleted. Also, the estimates and non-statistical assumptions of the statistical section should be supported by discussion in the background section.

The answer to this question should include:

-Study Design/Endpoints

- Recap of study objectives and endpoint definitions. An assessment of how study objectives will be assessed by identifying & defining which endpoints will be used to assess each component of the study objectives.
- The study design should include contingencies for early stopping, interim analyses, stratification factors (If applicable), and any characteristics to be incorporated in analyses.
- The power/precision of the study to address the major study endpoint(s), the assumptions involved in the determination of power/precision.

Study Design:

This study employs a randomized design in which one group of participants will be assigned to use the CloudConnect system and the other group to CGM using their insulin paramenters and treatments.

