another, this will be used as a variable in the comparison of mean glucose by CGM to evaluate whether there remained a difference in mean glucose once total daily steps was taken into account. Similarly, if there is an imbalance of key participant characteristics among participants who complete the study in one treatment group (such as higher proportion of multiple-daily-injection participants in the CloudConnect group), this will be considered as a variable in the multivariable ANOVA comparing mean glucose by CGM, as a secondary analysis.

5. What is your plan for secondary variable analysis?

- HbA1c
- Mean glucose by CGM
- Percent time in range 70-180 mg/dL
- Percent time in range 70-150 mg/dL
- Percent time <70 mg/dL
- Percent time >180 mg/dL
- Number of low BG
- Average daily insulin dose
- Average grams of carbohydrate entered
- Steps/day by Fitbit
- Questionnaires: Family Conflict Scale, Division of Diabetes Responsibilities, Child Self Management and My-Q scores.
- Response to weekly standardized questions:
 - i. *During the past week, did you talk with your parents about your diabetes management?*
(Yes=1, No=2)
 - ii. If you answered “yes,” how good or bad was the tone of that conversation?
(Likert scale: Very good = 1; good =2; Neutral = 3 bad =4; Very bad =5)
 - iii. During the past week, did you change your insulin parameters?
(Yes=1, No=2)

6. Have you been working with a statistician in designing this protocol?

No

7. Will data from multiple sites be combined during analysis?

No

Study Procedures-Biomedical Research

1. What will be done in this protocol?

PILOT STUDY:

Up to six adolescent subjects and six parent(s)/guardian(s) will be enrolled in a Pilot Study to assess the components used by the Experimental Group of the Main Study. This trial will evaluate if: (i) subjects can be trained to use study CGM + study Fitbit + personal pump (if pump user) or study insulin pen for mealtime

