Control Group: Personal insulin pump (if pump user) or study insulin pen (if MDI user) for mealtime bolus treatment + study CGM + study activity tracker (i.e. Fitbit). Both pump users and MDI subjects will use their personal insulin and insulin parameters during the trial. The Control Group will be trained to use the Study CGM in its full capacity, including setting alarms and using the CGM App that will permit the parent(s)/guardian(s) to receive high or low glycemic value alarms. Use of these alarms and apps will be optional for this group. These subjects will also be trained on the use of the activity tracker (i.e. Fitbit). The Control Group MDI subjects will be provided and trained on the use of an inPen (Companion Medical, San Diego, CA) for mealtime bolus treatments. Subjects will be asked to provide weekly downloads of all equipment, including the subject's personal insulin pump. Subjects may be asked to repeat a data collection week if the data provided is insufficient or poor quality.

Experimental Group: Personal insulin pump (if pump user) or study insulin pen (if MDI user) for mealtime bolus treatment) + study CGM + study activity tracker (i.e. Fitbit). Both pump users and MDI subjects will use their personal insulin and insulin parameters during the trial. The Experimental Group will be trained to use the Study CGM in its full capacity, including setting alarms and using the CGM App that will permit the parent(s)/guardian(s) to receive high or low glycemic value alarms. These subjects will also be trained on the use of the activity tracker (i.e. Fitbit). Experimental Group MDI subjects will be provided and trained on the use of an inPen (Companion Medical, San Diego, CA) for mealtime bolus treatments. Subjects will be asked to provide weekly downloads of all equipment, including the subject's personal insulin pump. Subjects may be asked to repeat a data collection week if the data provided is insufficient or poor quality. The Experimental Group will receive the additional CloudConnect component consisting of a weekly report based on analysis of the data gathered for each participant. After review by a study physician, the report will be sent via email once a week to both the adolescent participant and their parent(s)/guardian(s).

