Both groups will participate in the same number of visits (completed either in clinic or via phone or video conferencing) and follow up communication contacts done by phone calls, text messages and/or emails during the entire length of the trial. The production of the CloudConnect Report, in combination with the available Dexcom alarms and apps, is the study differential between groups.

*Secondary health outcomes: Average Blood Glucose values by Continuous Glucose Monitor; average total daily insulin; average carbohydrate of grams entered; number of insulin boluses; average number of steps by day

Figure 1: Study Design

There are four visits in the Main Study. Visit 1 and 2 may be combined and may be in person or via phone or video conference. A repeat Hemoglobin A1c will be collected if visit 1 and 2 are greater than 28 days. Visit 3 may be completed by phone. In addition, there will be weekly communication done by phone call, text message and/or email throughout the entire 12 weeks (3 months) of the data collection portion of the study. Method of weekly communications with the adolescent and parent will be based on participant/parent preference. The study team will communicate separately with the child and the parent in order to obtain their feedback independent of the other.

Subjects will be asked to electronically complete the following questionnaires at the completion of Visit 1 and repeated again at the conclusion of their study participation. Questionnaires may be answered remotely (i.e. at home) within a week of the visit or during a CRU visit.

- Blood Glucose Monitoring Communication questionnaire (Hood et al Diab Care 2004)
- Child and Parental Responsibility Questionnaire (adapted from Anderson et al J. Ped Psychol 1990)
- Child Self-Management
- Diabetes Care and Communication
- Diabetes Family Conflict Scale-Revised (Hood et al Diab Care 2007)
- Family Communication Inventory

- MY-Q (deWit et al Ped Diab 2012)
- Questions about CloudConnect use (CloudConnect group only, asked only at study end):
 - On a scale of 1-7, with 1 being very difficult and 7 being very easy, how easy was it to understand the information provided in the weekly reports? Can you tell me why you gave the score you did? What could have made the weekly reports easier to understand?

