Visit 2 (may be combined with Visit 1, may be done via phone or video): Adolescent subjects will be randomized and trained on the use of the study CGM and Fitbit. The CGM will be inserted into their abdomen per manufacturer instructions. Both Control and Experimental Group subjects will use their own personal pump. If the subject uses multiple daily injections (MDI), a commercially available Bluetooth connected insulin pen (inPen) will be given to both the Control and Experimental subjects in order to be able to collect the data accurately about meal time bolus treatments. Both pump users and MDI subjects will use their personal insulin. Each group will provide the study team weekly downloads from the study equipment and the personal insulin pump. Weekly CloudConnect reports will be provided to the Experimental Group participants *only*.

Depending on the subjects/family preference, the study team contact subjects via phone calls, text messages and/or emails at least once a week during the trial to:

- a) Remind them to download and transmit the data
- b) Check for AEs or SAEs
- c) Ask weekly standardized questions

All subjects will be reminded on how to download study data, if necessary. Both groups may complete a 1-week run-in period if they are CGM-naïve to ensure they are comfortable with the use of the study equipment, that all the study devices work properly, and to address issues related to transmission of the data to the study team. This run-in period may be repeated as necessary up to 3 times at the request of the study subject or study team. This data will not be included as part of the 12 week data collection. For subjects who have CGM experience, the investigator will determine if it is appropriate for he or she to skip the run-in period.

Visit 3 Check-in (Week 8 / on-site, email, or phone):

Subjects will download diabetes equipment weekly and submit the data to the study team for 12 weeks. Subjects may be asked to repeat a week of data collection if the quality of the data is insufficient for analysis.

A Check-In with the adolescent and parent/guardian will be completed to evaluate compliance and to answer any questions that the adolescent or parent may have about the study.

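### As written, the daily insulin outcome would combine total insulin for pump users with mealtime bolus insulin for injection users, because no source is described for long-acting doses

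*Combined protocol and SAP*

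**What the plan says.** - **Outcome.** Statistical Considerations item 5 lists "Average daily insulin dose" without a definition or data source. The note to Figure 1 (Study Procedures, Main Study) names it "average total daily insulin", so total insulin appears to be intended.
- **Analysis.** Item 4 compares secondary outcomes between arms by t-test. Multivariable ANOVA is a secondary analysis, used particularly when key variables differ between groups.
- **Pump users.** The group descriptions under Randomization state: "Subjects will be asked to provide weekly downloads of all equipment, including the subject's personal insulin pump".
- **MDI users.** Visit 2 says the pen is given "in order to be able to collect the data accurately about meal time bolus treatments". The inclusion criteria add: "MDI users should use Humalog® and Novolog® insulin to use in study insulin pen".
- **Long-acting insulin.** An exclusion criterion is "Use of long-acting insulin that is not Lantus or Tresiba", and the section on other drugs restricts "Use of anti-diabetic agents other than short-acting insulin for CSII subjects or long-acting insulin for MDI subjects". MDI users are therefore expected to take long-acting insulin, and it does not go through the study pen.
- **Weekly contact.** The download reminder covers CGM, pump or pen, and Fitbit. The weekly question on insulin asks, yes or no, whether parameters changed. It asks for no dose.

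**The concern.** One label covers two quantities. For a pump user the download gives the whole daily dose. For an MDI user the described data give rapid-acting mealtime insulin only. Three things follow if the plan is carried out as it reads:

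- The pooled mean is neither total insulin nor bolus insulin, so it cannot be interpreted as daily dose.
- The artificial gap between therapies enters the error variance of a t-test that ignores therapy.
- The size of any long-acting dose change in MDI users is not measured. This matters because the Background says the weekly report relates risk periods to insulin dosing behavior, so dose is a natural readout of whether families acted on it.

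Long-acting doses that are not recorded during the 12 weeks cannot be reliably recovered afterwards.

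**Working it through.** The plan gives no expected value, SD or power for this outcome, so there is no stated figure to reproduce. The check has two parts.

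**1. Data sources side by side**

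| | Pump (CSII) | MDI |
|---|---|---|
| Insulin taken | Short-acting, by pump | Rapid-acting by study pen, plus long-acting outside it |
| Source described | Weekly pump download | Weekly pen download |
| Quantity obtained | Total daily insulin | Mealtime bolus insulin |

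Share of the sample affected: Statistical Considerations item 1 sets a minimum of 10 in each of four age-by-therapy subgroups, two of them insulin pen, so at least 2 × 10 = 20 of 80 completers (25%). Item 3 aims for equal pump and MDI numbers, which would give about 40 of 80 (50%).

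**2. Illustration of size**

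Assumptions, none from the documents: true total dose T = 50 U/day in both therapies; SD s = 15; long-acting share L = 0.4 to 0.6 of an MDI user's total; a true arm difference D = 5 U, spread proportionally over long-acting and bolus insulin; two-sided alpha 0.05. From the plan: 40 completers per arm, and MDI share p = 0.5 or 0.25.

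- Average MDI shortfall = T × L = 20 to 30 U.
- Observed difference = D × (1 − pL).
- Within-therapy variance = (1 − p)s² + p[s(1 − L)]².
- Between-therapy variance = p(1 − p)(TL)².
- Pooled SD = square root of the sum; SD with therapy in the model = square root of the within-therapy part.

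For p = 0.5 and L = 0.4: within = 0.5 × 225 + 0.5 × 81 = 153; between = 0.25 × 400 = 100; pooled SD = √253 = 15.9; SD with therapy in the model = √153 = 12.4; observed difference = 5 × 0.8 = 4.0 U.

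| MDI share | L | Observed difference (U) | Pooled SD (U) | Power, pooled t-test | SD, therapy in model (U) | Power, therapy in model |
|---|---|---|---|---|---|---|
| 50% | 0.4 | 4.0 | 15.9 | 20% | 12.4 | 30% |
| 50% | 0.5 | 3.75 | 17.2 | 16% | 11.9 | 29% |
| 50% | 0.6 | 3.5 | 18.9 | 13% | 11.4 | 27% |

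If true total dose were measured in everyone (5 U, SD 15, 40 per arm), power would be 31%. At p = 0.25 the pooled t-test gives 17-23%.

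Two further results under the same assumptions:

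- If the 5 U change fell entirely on long-acting insulin (basal delivery in pump users), MDI users would show 0. At p = 0.5 the pooled difference would be 5 × 0.5 = 2.5 U. No covariate recovers this.
- A 10-point difference between arms in the MDI share would by itself produce 0.10 × T × L = 2 to 3 U in the unadjusted comparison.

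**The case against.** A reader might go further in four ways, and the documents do not support any of them.

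- **That long-acting doses definitely go unrecorded.** The plan does not say so. The list of downloads appears in a reminder, not in a data specification; the Main Study weekly questions are introduced as including those listed; and a case report form outside these documents could hold the doses. What stands is that no source is described.
- **That the arm comparison is seriously biased.** Insulin therapy is a randomization stratum with blocks of 4, so the MDI share should be close in the two arms. Items 4 and 5 of the statistical section also foresee an MDI imbalance among completers and allow for it in a secondary ANOVA, though the example given is mean glucose. What stands is that unequal dropout, with 20-30% expected, could still produce some bias in the t-test.
- **That long-acting changes are wholly invisible in MDI users.** Adolescent and parent are both asked weekly whether insulin parameters changed, and the adolescent's answer is a listed secondary outcome. It records neither the size of a change nor which insulin changed.
- **That the missing doses cause the power loss.** Most of the illustrated loss is variance between therapies, which disappears once therapy is in the model (27-30% against 31%).

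It is also fair to say that the outcome is one of many secondary ones, carries no stated hypothesis, and would be underpowered for 5 U under these assumptions even if measured perfectly.

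**Conclusion.** The point holds as a gap between the named outcome and the data the plan describes. Carried out as written, daily insulin would be total dose for pump users and mealtime bolus dose for MDI users, in 25-50% of the sample on the plan's own enrolment targets. The result would not be interpretable as daily insulin, its variance would be inflated, and the size of long-acting changes in MDI users would be lost.

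The conclusion rests on an inference from the pen's stated purpose, the insulins used in it, and the absence of any other described source. If long-acting doses are in fact collected elsewhere, stating the source and definition removes the measurement problem; therapy should still be in the analysis. All unit and power figures are illustrative and depend on the assumed dose, SD, long-acting share and effect. The primary FCI analysis is unaffected, so this is a correction to a secondary outcome.

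**What to change.** **Preferred.** Add one item to the existing weekly contact recording the long-acting doses each MDI subject took that week. Define the outcome in Statistical Considerations item 5 as total daily insulin, with the source named for each therapy: pump download, or pen download plus the weekly item. Include insulin therapy, already a randomization stratum, in the main comparison of this outcome and not only in a conditional secondary analysis.

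**If long-acting doses will not be collected.** Rename the outcome as pump- or pen-recorded bolus insulin and analyse it within the CSII and MDI strata. The strata matter here because a pump may log boluses that a mealtime pen does not. Report total daily insulin in CSII subjects only, and reconcile the note to Figure 1 with item 5.

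**Cost.** The preferred route costs one extra weekly item, self-reported and so less exact than a device record. The fallback is mainly a wording change, but it leaves total insulin available only in pump users (about 20 per arm at an equal split, with about 18% power for 5 U at SD 15) and still does not measure long-acting changes in MDI users. Neither route alters any treatment.
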